9.0 Radiotherapy

Radiotherapy schedule for Cohort 1 and Cohort 2

WEEK	WEEK 2						WEEK 3						WEEK 4						
	1	2	3	4	5	6	7	8	9	10	11	12	13	14	15	16	17	18	19
DAY #	M	T	W	T	F		M	T	W	T	F		M	T	W	T	W	T	F
Tx	wb/c	wb/c	wb	wb	wb		wb	wb	wb	wb	wb		wb	wb	wb	wb	wb	wb	
	w*	w	TB	TB	TB		TB	TB	TB	TB	TBB		TB	TB	TB	TB	TB	TB	
	TB+	TB									BBb							B	

*wb = target is whole breast, chest wall or reconstructed breast, 2.7 Gy/fraction

+TB = target is the original tumor bed or mastectomy scar in post-mastectomy patients without reconstruction, 3.2 Gy/fraction

Cohort 2 will follow the same schedule like Cohort 1 but level III axillary and SCV nodes will also be treated daily, at 2.7 Gy per fraction, to a total dose of 40.50 Gy.

9.1 Radiotherapy target

Patients with sentinel node negative or axillary node dissection negative results will be assigned to cohort 1. Patients with sentinel node positive or axillary node dissection positive results will be assigned to cohort 2. Patients with more than 5 nodes involved at axillary dissection will be excluded from this study since they will be eligible to receive radiotherapy to level I and II axilla.

9.2 Dose Specification

Patients will receive 15 daily radiation fractions of 2.7 Gy, to the entire breast, to a total dose of 40.5 Gy to the breast, and an additional .50 Gy to the tumor bed or chest wall scar daily to a total dose of 48 Gy to the tumor bed or chest wall scar. The whole breast or chest wall and boost volume will be treated for five consecutive fractions Monday to Friday for 3 weeks. Patients undergoing nodal RT will also receive 2.7 Gy to the nodal targets, daily, Monday to Friday to a total dose of 40.50 Gy.

All patients will be CT scanned in the prone position on a specially designed board that allows the indexed breast tissue to fall freely below the board, granting unobstructed access to the breast and lymph nodes through radiation ports from multiple beam angles. CT slice thickness should be 5 mm or less. Prior to the patient lying prone on the table for scanning, the borders of the field will be marked with radio-opaque CT fiducial markers. The chest wall scar will also be delineated using radio-opaque fiducial markers.

These markers will be used to outline the treatment volume according to conventional treatment guidelines. Borders of the fields will be set medially at mid-sternum, laterally at the anterior edge of latissimus dorsi, superiorly at the bottom of the clavicular heads and inferiorly 2 cm from the infra-mammary fold. Patients will be tattooed with leveling marks for setup alignment with room lasers and for positioning the isocenter of the beams. A tattoo will be placed on the lateral breast tissue as a landmark for planning and positioning.

Contouring of tumor bed, indexed and contralateral breast tissue, thyroid, ipsilateral and contralateral lung, heart and left anterior descending artery (LAD) will be performed in order to guide beam arrangement and optimal normal tissue avoidance. The patient will be CT scanned in the supine position if the patient cannot lie prone, or if the prone plan is not acceptable. Specifically supine set up will be attempted if the dosimetry information derived from prone planning reveals exceeding normal tissue dose constraints for heart, LAD, ipsilateral lung, or contralateral lung (see section 8.7.8.4)

9.3 Target Delineation

The PTVBreast is the entire breast volume acquired in prone or supine position based on physician's delineated fields. The PTVBreast is derived from the 50% isodose line associated with clinically determined opposed tangent fields. This is accomplished by converting the 50% isodose level to a structure, smoothing and then removing parts extending outside the 50% isodose structure with an additional 0.7 cm margin within the field borders. The lung and the heart are also excluded from the PTVBreast volume. 3-dimensional/intensity modulated RT (IMRT) tangents will include the breast/chest wall, and coverage of breast will be ensured by placing the posterior edge of the field on a plane connecting the midline to the anterior extent of the latissimus dorsi. Planning target volume (PTV) of the breast/chest wall will be created from the volume contained in the tangent fields with an additional 6 mm subtracted in all directions. The tumor bed/boost volume will be contoured with a 10-mm expansion. The regional nodal clinical target volume includes ipsilateral supraclavicular and level III axillary lymph nodes, with a 5-mm expansion (PTV nodes), but cropped 6 mm from the skin. We anticipate that coverage will require 3 IMRT fields (2 anterior/1 posterior). All target volume and normal tissue constraints are shown in Table 1. Portal images of orthogonal set-up fields will be acquired on days 1 through 3, then weekly. Portal imaging of each treatment field will occur once during the first 3 days of treatment. Cone beam computed tomography of PTV nodes is acquired on days 1 through 3.

9.3.1 The GTV is the tumor bed, as identified on CT.

9.3.2 The PTVTumor is the GTV with an additional 1.0 cm3D margin.

9.3.3 PTVTumor will not extend outside of the breast tissue and, **Table 3.**

if necessary, will be consistently modified (“clipped”) to be confined within PTVBreast.

9.4 Normal structure delineation

The following structures will be contoured: contralateral breast, thyroid, ipsilateral lung, contralateral lung, heart, and LAD. If nodes are treated spinal cord, esophagus and brachial plexus will also be contoured Table 3 describes the constraints.

Technical Factors

- 9.5.1 Dose calculation with heterogeneity corrections must be used.
- 9.5.2 Nominal photon energies greater than or equal to 6 MV must be used. 16 MV photons may be used mixed with 6 MV photons in a ratio not to exceed 3:1 (16 MV: 6 MV). However, 16 MV photons may not be used for any beam in which the superficial extent of the GTV is within 0.5 cm of the skin.
- 9.5.3 Prone positioning requires the isocenter to be placed approx 1.5 cm from medial edge of the breast to allow clearance between the gantry and the couch/board.
- 9.5.4 Hybrid Whole Breast planning - IMRT (intensity modulated radiation therapy) tangents plus non-IMRT tangents
 - 9.5.4.1 Non-IMRT tangents deliver nominally 67% of prescribed dose using 6 MV or 6MV/16MV photons and include 3 cm anterior flash. The fields are wedged and weighted to obtain a uniform dose distribution, normalized to allow approximately 105% dose max.
 - 9.5.4.2 IMRT tangents deliver nominally 33% of prescribed dose using 6 MV photons and include 3 cm anterior flash, and use the non-IMRT tangent plan as a base for optimization.

9.5.5 3D-CRT Whole Breast Planning

- 9.5.5.1 3D-CRT tangents will be used to obtain a uniform dose distribution. Wedges and/or field within fields can be used.

9.5.6 Boost plan

- 9.5.6.1 Non-coplanar beam arrangement is encouraged, but not required
- 9.5.6.2 Electrons, 3D-CRT or IMRT may be used
- 9.5.6.3 If the tumor bed, as visualized in the BEV (beams-eye-view), is within 1cm of the body surface, 1 cm of flash will be added to the field(s)
- 9.5.6.4 No photon beam will be directed toward heart, lung, contralateral breast, or thyroid
- 9.5.6.5 Inclusion of soft tissue not irradiated by the whole breast tangents is allowed to aid in target coverage

9.5.7 Composite plan is created with all fields. Dose Constraints

Target/Normal Tissue Dose specifications	
Target Volume/Normal Tissue	Dose Constraints
PTVTumor	V48 Gy \geq 98%
PTVBreast/Chest Wall	V40.5 Gy \geq 95%
PTVNodes	V38.5 Gy \geq 95%
Heart	V5 Gy $<$ 5%
Ipsilateral Lung	V10 Gy $<$ 20%
Spinal Cord	37.5 Gy maximum*
Esophagus	36 Gy maximum*
Brachial Plexus	42 Gy maximum*

9.5.7.1 Target volume dose constraints for Whole Breast Plans:

9.5.7.2 Whole breast IMRT hybrid tangents

9.5.7.3 PTVBreast max 108% (to $\geq 1\text{cc}$) of the whole breast dose. This can be achieved with 6 MV, or 6 MV/16 MV (IMRT/3D) photons.

9.5.7.4 PTVBreast: $\geq 95\%$ of the volume must receive $\geq 100\%$ of the whole breast dose.

9.5.7.5 PTVTumor: $\geq 98\%$ of the volume must receive $\geq 100\%$ of the whole breast dose.

9.5.7.6 Whole breast 3D-CRT tangents

9.5.7.7 PTVBreast max 112% (to $> 1\text{cc}$) of the whole breast dose.

9.5.7.8 PTVBreast: $\geq 95\%$ of the volume must receive $\geq 100\%$ of the whole breast dose.

9.5.7.9 PTVTumor: $> 98\%$ of the volume must receive $> 100\%$ of the whole breast dose.

9.5.7.10 Target volume dose constraints for Boost Plans:

9.5.7.11 IMRT Boost

9.5.7.12 Breast max 108% (to $> 1\text{cc}$) of the boost dose. This can be achieved with 6 MV IMRT, or a hybrid approach using 6 MV/16MV (IMRT/3D) photons.

9.5.7.13 PTVTumor: $> 98\%$ of the volume must receive $> 100\%$ of the total boost dose.

9.5.7.14 $> 60\%$ of the PTVBreast volume must not receive $> 50\%$ of the total boost dose.

9.5.7.15 3D-CRT Boost

9.5.7.16 Breast max 112% (to $> 1\text{cc}$) of the boost dose. This can be achieved with 6MV, 16 MV, or 6MV/16 MV photons.

9.5.7.17 PTVTumor: $\geq 98\%$ of the volume must receive $\geq 100\%$ of the total boost dose.

9.5.7.18 $> 60\%$ of the PTVBreast volume must not receive $> 50\%$ of the total boost dose

9.5.7.19 Composite of tangents and boost fields

9.5.7.20 PTVTumor: $> 98\%$ of the volume must receive $> 100\%$ of the total dose, where total dose is the whole breast dose plus boost dose.

9.5.7.21 PTVBreast: $> 95\%$ of the volume must receive $> 100\%$ of the whole breast dose.

9.5.7.22 PTVBreast: no more than 60% of PTVBreast should receive $> 4455\text{ cGy}$

9.5.7.23 Normal tissue dose constraints:

9.5.7.24 Heart: $< 5\%$ of the heart receives $> 5\text{ Gy}$.

9.5.7.25 Ipsilateral lung: $< 15\%$ of the ipsilateral lung receives $> 10\text{ Gy}$.

9.5.7.26 Contralateral lung: $< 15\%$ of the contralateral lung receives $> 5\text{ Gy}$.

9.5.7.27 LAD: maximum $< 1800\text{cGy}$, mean $< 1000\text{ cGy}$.

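### Section 9.5.7 gives two unreconciled limits for ipsilateral-lung V10 (under 20% in the constraints table, under 15% in item 9.5.7.25), so a plan between them meets one and exceeds the other

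*Combined protocol and SAP*

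**What the plan says.** Two places in section 9.5.7 set a limit on ipsilateral-lung dose.

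- The table that opens the section, under the line "Composite plan is created with all fields. Dose Constraints", has a row for the ipsilateral lung: V10 Gy below 20%.
- Further down, the list introduced as "9.5.7.23 Normal tissue dose constraints" has item 9.5.7.25: less than 15% "of the ipsilateral lung receives" more than 10 Gy.

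Three other places refer to the constraints.

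- Section 9.2 uses them to decide when to try another position: "Specifically supine set up will be attempted if the dosimetry information derived from prone planning reveals exceeding normal tissue dose constraints". It names heart, LAD, ipsilateral lung and contralateral lung, and points to section 8.7.8.4.
- Section 9.3 says "All target volume and normal tissue constraints are shown in Table 1".
- Section 9.4 says "Table 3 describes the constraints", where it means Table 3.

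**The concern.** A planner needs one acceptance limit for each organ and dose level. Here the same organ at the same dose level has two, both in current text and a short distance apart. For some plans the protocol therefore gives two answers to whether the lung constraint is met. Section 9.2 attaches an action to exceeding a lung constraint, so the question reaches the choice of treatment position as well as the sign-off of a plan. The limit protects normal tissue, so the text should leave no doubt about which figure applies to whom.

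**Working it through.** No sample-size or power formula is involved. The check sets the two lists side by side, works out which plans they treat differently, and then asks whether any cross-reference settles the matter.

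**Side by side**

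| Structure | Table in 9.5.7 | List 9.5.7.24 to 9.5.7.27 |
|---|---|---|
| Heart | V5 Gy < 5% | < 5% receives > 5 Gy |
| Ipsilateral lung | V10 Gy < 20% | < 15% receives > 10 Gy |
| Contralateral lung | no row | < 15% receives > 5 Gy |
| LAD | no row | maximum < 1800 cGy, mean < 1000 cGy |
| Spinal cord, esophagus, brachial plexus | maximum doses given | no item |

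The heart limit is the same in both. The two lists therefore overlap in scope, and the ipsilateral lung is the one normal structure that they share and disagree on.

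**Which plans are affected**

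Let V be the percentage of ipsilateral lung receiving more than 10 Gy.

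- V < 15%: meets both limits.
- 15% ≤ V < 20%: meets the table, exceeds 9.5.7.25.
- V ≥ 20%: exceeds both.

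The zone of disagreement is 20 − 15 = 5 percentage points wide. A plan with V = 17%, for example, is acceptable under the table and an exceedance under 9.5.7.25. Because 15% is less than 20%, any plan that meets 9.5.7.25 also meets the table.

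**Do the cross-references settle it?**

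- Section 9.2 speaks of a prone plan that "reveals exceeding normal tissue dose constraints for heart, LAD, ipsilateral lung, or contralateral lung (see section 8.7.8.4"). Those four structures are exactly the ones in 9.5.7.24 to 9.5.7.27, and two of them have no row in the table. This suggests that 9.2 has the list in mind. But the section number it gives does not exist in the document.
- Section 9.3 says that all constraints are in Table 1, and section 9.4 says that they are in Table 3. Both seem to mean the table in 9.5.7, but they number it differently.

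So 9.2 appears to lead to the 15% figure and 9.3 and 9.4 to the 20% figure, and none of the three pointers is clean enough to decide between them.

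**The case against.** **The table may be for nodal plans and the list for non-nodal plans.** This is the best counter-argument. The table carries rows for the nodal target, spinal cord, esophagus and brachial plexus, and section 9.4 has those three organs contoured only when nodes are treated. The 9.5.7 list deals with whole-breast, boost and composite tangent-plus-boost plans and has no nodal entry. Missing labels are therefore a plausible explanation. It is not an established one. The table also holds the tumor-bed, breast/chest wall and heart rows, which are not specific to nodal treatment. Section 9.3 presents the constraints table as complete, and section 9.2 applies a single trigger to all patients.

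**Both limits can be met at once.** This is true, because one is nested in the other. But the protocol contains no rule of precedence, and a plan in the 15% to under 20% zone still gets two verdicts.

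**A scope note may have been lost from the table.** Some entries carry asterisks with no footnote visible in the text available. The lung row has none, so this is a reason for some caution and does not explain the difference.

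**A reader might infer wider consequences.** The documents do not support these:

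- *That the prone/supine choice rests on lung V10.* It is one trigger among several. Section 9.2 also names three other structures and patients who cannot lie prone. Section 2.3 separately requires a supine simulation if prone tangents include any heart or more than 5% of lung volume, which is a different metric. Patients whose internal mammary nodes are treated are set up supine in any case.
- *That a dosimetric-compliance result is at risk.* Compliance with dosimetric constraints is not among the endpoints in section 16.1. It was a secondary endpoint of the earlier nodal trial described in section 2.5.
- *That the two sites added in Version 5.0 make divergent readings more likely.* The summary of changes adds them for enrollment and does not say that planning is done there.

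**Conclusion.** The inconsistency is real and should be corrected. It is a contradiction in a stated safety limit, not a matter of missing detail or of a debatable design choice. It is confined to plans with ipsilateral-lung V10 from 15% to under 20%, and it acts in one direction only.

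How many plans fall in that zone is unknown, because the documents give no distribution of V10. The practical reach is plan acceptability and one of the section 9.2 triggers. The dermatitis endpoint, the 37 patients per cohort and the planned analysis do not depend on it.

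The conclusion assumes that both figures are read correctly from the text and that no scope note is missing from the table. If a nodal/non-nodal split was intended, the point becomes one of absent labels, and the remedy is the same. No view is taken on which limit is clinically right.

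**What to change.** Reconcile the table in 9.5.7 with item 9.5.7.25. Either one ipsilateral-lung limit appears in both places, or two limits are kept and each is labelled with the cohort or plan type it governs. The sponsor's clinical and physics team decides which limit applies to whom.

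In the same edit, replace the reference to section 8.7.8.4 in 9.2 with the correct location, and give the constraints table one number that 9.3 and 9.4 both use, so that all three sections lead to the reconciled limit.

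The cost is a protocol clarification. No additional patients or data are needed, and the statistical section does not change.

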9.6 Boost Technique with Image Guidance (IGRT)

IGRT Target Localization: Cone-beam CT (CBCT) images will be acquired weekly prior to each boost treatment. By using IGRT to image the post-operative tumor bed of the breast in “real-time”, the operator may automatically align the tumor bed with the treatment machine on each day of treatment of the tumor bed. If the resection cavity is not visualized then cone-beam CT images will be used to ensure optimal positioning of the breast tissue. A portal image of each boost treatment field will be acquired following CBCT.

9.7 Dosing Delays/Dose Modifications

For radiation toxicity: In case of grade 3 acute skin toxicity occurring during the course of the 3 weeks radiotherapy treatment, the dose per fraction of the remaining treatment fractions will be reduced to 2 Gy/fraction to the whole breast (and 2 Gy to the boost area on boost days) until completion of the total prescribed dose. No interruptions are planned. No other grade 3 toxicity is expected.

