Based on the experience gathered from NYU Protocol 05-181, it is rational for all patients to first undergo a CT Simulation in the prone position. In this protocol, we will again use 2.5 mm slice thickness with the patient positioned on a dedicated breast mattress that allows the index breast to freely fall through an opening. If it is found that conventional tangents in the prone position include **any** volume of heart and/or > 5% of lung volume, a second simulation will be required in supine position to assess which position best minimizes the amount of heart and lung in the treatment fields to be chosen for treatment.

2.4 NYU 09-0300: A Prospective Randomized Trial Aimed At Establishing The Optimal Boost Schedule

Radiobiological evidence supported the introduction of a larger fraction dose before a two-day treatment break (weekend). We studied two different boost schemas in a randomized trial of 400 patients. The **standard arm** was a concomitant boost protocol over three weeks which had previously been evaluated in over 500 patients (NYU 03-30 and NYU 05-16 of 60

181) and had shown excellent tolerance, and results. In addition to the 2.7 Gy whole breast dose, an additional 2 Gy was delivered to the tumor bed on each of the three Fridays, with the tumor bed receiving 4.7 Gy on each of the three Fridays.

At a median follow-up of 45 months, there were no deaths related to breast cancer. The weekly boost regimen produced no more grade ≥ 2 acute toxicity than the daily boost regimen (8.1% vs 10.4%; non-inferiority $Z = -2.52$; $p = 0.006$). There was no statistical difference in cumulative incidences of long term fibrosis or telangiectasia grade ≥ 2 between the two arms (log-rank $p=0.923$). There were 2 local and 2 distant recurrences in the daily boost arm. There were 3 local and 1 distant recurrences in the weekly arm, with no difference in 4-year RFS between the two arms (98% in both arms). In addition, extensive QOL assessment between the 2 arms demonstrated comparable results with regard to the patient's experience during and after radiotherapy. In conclusion, the trial demonstrated that a tumor bed boost delivered either daily or weekly is similarly tolerated during accelerated prone breast radiotherapy, with excellent control of disease and comparable cosmetic results (7).

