15.2 Stopping rules

Treatment will be held if patients experience > Grade 2 radiation dermatitis. Patients will be monitored until the resolution of the adverse event. Based on PI's discretion, patients will resume or be withdrawn from the study. Adverse Events will be recorded based on CTCAE v4.03.

If safety concerns arise, the DSMC will identify these concerns and recommend modification or termination of the clinical trial. There is no formal interim analysis for this trial.

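### For grade 3 dermatitis during treatment, sections 9.7 and 15.2 give incompatible orders, and 9.7's boost wording does not fit a 0.5 Gy boost at every fraction

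*Combined protocol and SAP*

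**What the plan says.** **Grade 3 during treatment.** Section 9.7 (Dosing Delays/Dose Modifications) applies when grade 3 acute skin toxicity appears within the three weeks of radiotherapy. The remaining fractions go down to 2 Gy to the whole breast, "and 2 Gy to the boost area on boost days) until completion of the total prescribed dose. No interruptions are planned". Section 15.2 (Stopping rules) says: "Treatment will be held if patients experience > Grade 2 radiation dermatitis". The patient is then watched until the reaction resolves, and at the principal investigator's discretion "patients will resume or be withdrawn from the study". Neither section refers to the other.

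**Boost.** Section 9.2 prescribes 2.7 Gy to the breast at each of 15 fractions and "an additional .50 Gy to the tumor bed or chest wall scar daily". The schedule in section 9.0 lists the tumor bed or "mastectomy scar in post-mastectomy patients without reconstruction, 3.2 Gy/fraction". The Protocol Summary exempts reconstructed patients from the boost.

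**The concern.** Grade 3 lies above grade 2, so one on-treatment event triggers both rules. Staff who open 9.7 would treat the next day at a lower dose. Staff who open 15.2 would stop. Section 15.2 also gives no dose for a patient who resumes.

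The boost phrase adds a second uncertainty. It speaks of boost days, but here every treatment day is one, and no 2 Gy boost is prescribed anywhere in the regimen. The clinician has to guess what the tumor bed or scar should receive in a patient whose skin has already broken down. At stake are delivered dose, treatment duration and safety in those patients.

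**Working it through.** **1. The planned doses reproduce.** From section 9.2: breast 15 × 2.7 = 40.5 Gy; boost 15 × 0.5 = 7.5 Gy; tumor bed or scar per fraction 2.7 + 0.5 = 3.2 Gy; total 15 × 3.2 = 48 Gy. All match the text.

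**2. The two rules side by side, for grade 3 dermatitis during the course.**

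| | Section 9.7 | Section 15.2 |
|---|---|---|
| Next fraction | given, at 2 Gy | not given until resolution |
| Interruption | none planned | required |
| Dose afterwards | 2 Gy per fraction to the breast | not stated |
| End of treatment | full prescribed dose | resumption or withdrawal |

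Holding and then resuming at 2 Gy meets every line of 9.7 except the one on interruptions. Withdrawal does not meet the last line either.

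**3. What the boost phrase implies.** After k fractions, breast dose left = 40.5 − 2.7k, tumor-bed dose left = 48 − 3.2k, and boost left = 7.5 − 0.5k. Section 9.3.3 clips the tumor-bed target "to be confined within PTVBreast", so the bed also receives the breast dose.

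| k | Fractions planned | Breast left; fractions at 2 Gy | Bed left; fractions at 2 Gy total | Boost left; boosts of 2 Gy |
|---|---|---|---|---|
| 5 | 10 | 27.0 Gy; 13.5 | 32.0 Gy; 16.0 | 5.0 Gy; 2.5 |
| 10 | 5 | 13.5 Gy; 6.75 | 16.0 Gy; 8.0 | 2.5 Gy; 1.25 |
| 12 | 3 | 8.1 Gy; 4.05 | 9.6 Gy; 4.8 | 1.5 Gy; 0.75 |

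- *Total reading.* The bed receives 2 Gy per fraction, down from 3.2. With k = 10 it stands at 32 + 13.5 = 45.5 Gy when the breast reaches 40.5 Gy. The last 48 − 45.5 = 2.5 Gy can go to the boost area alone.
- *Additive reading.* The bed receives 2 + 2 = 4 Gy on a boosted fraction, and 4 / 3.2 = 1.25, so 25% more than planned. If the bed stops at 48 Gy, the 2.5 Gy of boost left at k = 10 covers 1.25 such boosts, so only one or two fractions are involved.

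**4. How many patients.** Grade 3 dermatitis occurred in 2 of 90 patients in the trial of section 2.2, and in none of 70 treatments in the trial of section 2.5. Applied to 74 patients: 74 × 2/90 = 1.6 and 74 × 0/70 = 0.

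**5. Primary endpoint.** Section 16.6.1 counts dermatitis of grade II or greater within 60 days of the end of treatment. A patient who triggers either rule is already an event, and section 16.2 keeps every registered patient in the analysis.

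**The case against.** **The rules may run in sequence.** One can read 15.2 as the first step and 9.7 as the dose on resumption, with the sentence on interruptions as a statement of intent. That is a sensible plan and may be what was meant. But the section a treating team would consult about delays foresees no interruption, while the other section requires one, so the text cannot be followed as it stands.

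**The boost phrase has a natural reading.** Section 9.7 describes a reduction. It also lacks the word that section 2.4 uses for the earlier trial's weekly schedule: "an additional 2 Gy was delivered to the tumor bed on each of the three Fridays". A total of 2 Gy is therefore much the better reading, and this stands. A reader might infer that the protocol orders a dose increase on injured skin; the documents do not support that. The 4 Gy reading is only one that the wording fails to exclude.

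**The totals are stated.** A reader might also fear that the bed overshoots 48 Gy or loses its boost. Section 9.7 continues to the total prescribed dose, and section 9.2 fixes that at 40.5 Gy and 48 Gy. Different fraction counts for breast and bed follow from the total reading and are not an error in themselves.

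**The origin of the phrase is unproven.** It resembles the earlier Friday boost, but carry-over is an inference. Section 9.6 has cone-beam images "acquired weekly prior to each boost treatment", which might suggest a weekly boost; there the word describes the imaging, and the same section speaks of alignment on each day the tumor bed is treated.

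**Silence elsewhere is missing detail.** Section 9.7 does not mention the Cohort 2 nodes, and 15.2 does not say whether withdrawn patients keep their late-toxicity visits. The schema's statement that all patients are followed, and the quality-of-life instructions in Appendix 3.2 for patients who stop therapy, narrow the second gap. Neither is an error.

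**Conclusion.** Wrong as written, but minor. Sections 9.7 and 15.2 give incompatible instructions for the same on-treatment event, and the boost phrase describes neither the dose nor the schedule of this regimen. Both follow from the text and need no assumption about intent.

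The likely reach is about 0 to 2 of 74 patients. That rests on small counts from the adjuvant setting, graded on different scales (RTOG in one trial, CTCAE version 3.0 in the other), carrying over to patients treated after neo-adjuvant therapy. The post-mastectomy patients in the second trial had no boost, whereas here the unreconstructed scar receives one. In the other direction, section 2.2 reports that dermatitis tended to appear in the week after treatment ended, when neither rule applies. The boost part concerns only patients who receive a boost.

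A reader might infer that the primary result is at risk. It is not: the effect is on delivered dose and safety, and the primary event count is essentially unchanged.

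**What to change.** Put one identical grade 3 rule in sections 9.7 and 15.2. The clinical investigators should choose between:

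- holding until resolution, then resuming at 2 Gy per fraction or withdrawing the patient from protocol treatment, with the sentence on interruptions deleted; or
- continuing at 2 Gy per fraction, with the hold deleted.

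Replace the boost phrase with an explicit total dose per fraction to the tumor bed or scar. It must be below 3.2 Gy, since a ceiling at 3.2 Gy would allow no reduction at all; if the natural reading is the intended one, write 2 Gy in total. Add that any boost still owed when the breast reaches 40.5 Gy is given to the boost area alone, up to 48 Gy. The same edit could usefully state the nodal dose for Cohort 2.

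The cost is a few sentences by amendment, with no extra patients, visits or procedures.
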